In Colombia, according to the 2005 and 2010 ENSIN surveys, the majority of the population consumes oil-fried foods, has a low consumption of fruits, vegetables, fish and high consumption of processed and ultra-processed products. This diet profile is characteristic of western culture, with low intake of food sources of essential fatty acids (EFA), fat-soluble vitamins, fiber and phytonutrients. A good alternative to increasing the consumption of EFA, and preventing the development of CVD with food, is to add or enrich mass consumir products such as dairy derivatives, as these foods are considered by the majority

According to data in the ENSIN of 2015, dairy products are frequently consumed by Colombians, where the estimated milk intake for the population is 94.2% in a regular month and 94.2% for dairy derivatives such as cheese, yogurt and kumis (Ministerio de salud, 2015). Comparing these data with the one from the ENSIN of 2010, we can observe an increase in the consumption of milk and dairy derivatives since it went from 85.5% to 93.4% respectively (Minesterio de Protección Social, 2010). Similarly, the Fondo

 
Pontificia Universidad JAVERIANA Colombia
	
Research registration PUJ
	
Version: 1

Investigation project
		

Nacional del Ganado FNG (Fedegan) reported that between 2010 and 2014, milk consumption increased by 3.6 litres, from 139.4 litres per person to 143 litres a year; and of the 1.715 million litres of milk produced, about 26% of the total production, are devoted to the production of regional cheeses. Additionally, fermented beverages such as yogurt, move around \$470 million and is expected to bill \$602 million by 2023. Its main leaders are Alpina, Yogo Yogo and Bonyurt, with shared of 18.1%, 17.8% and 14.4% respectively. These are followed by Regeneris and Algarra (Euromonitor, 2019).

Food sources of omega 3 are mainly vegetable oils and marine foods such as fish, fish oils, and algae. While the sources of vitamin E in the form of tocotrienol are mainly palm oil and achiote. Usually in the western culture, these foods are not regularly consumed, which causes the industry to look for alternatives to transport these compounds into mass consumption foods, such as milk and dairy products.

Milk and dairy products have an adequate nutritional profile, thanks to their content of protein, calcium, riboflavin, among other nutrients (Alvídrez-Morales, A, González-Martínez, B.E., Jiménez-Salas, 2002; Santillan Urquiza, Mendez Rojas, & Vélez Ruiz, 2014). Strategies such as reducing sodium chloride (NaCl) in cheeses and decreasing the fat content in milk and derivatives have been implemented to combat some diseases such as hypertension and dyslipidemia (Millone, Olagnero, & Santana, 2011).

Dairy products can be vehicles of bioactive compounds, adding, replacing and/or reducing the most variable component, the lipid fraction. Therefore, some vegetable sources with adequate EFA profiles and vitamin content with antioxidant effect such as vitamin E, are of interest in the development of functional foods (FF), as they can be used as ingredients to improve the fat profile of milk-derived foods.

In Colombia, Sacha Inchi and Palma crops are an alternative to the replacement of illegal crops, as the processing of their fruits represents an economic opportunity for the sustainable development of vulnerable communities, in the context of the post-conflict- Sacha Inchi (*Plukenetia volubilis* L.) is a plant with great economic potential thanks to the transformation of its fruit (seeds) into products of high added value, mainly the oil containing 50% ALA (18:3ω-3), 36.8% AL (18:2ω-6) for an omega 3: omega 6 ratio of 0.76 and a total tocols content of 211.8 mg/100g (Wang, Zhu, & Kakuda, 2018). The ω-3:ω-6 ratio is desirable to reduce the risk of developing several chronic diseases of high prevalence, such as cardiovascular diseases, cancer, and inflammatory and immune diseases (Vanegas-Azuero & Gutiérrez, 2018), and that is why this oil is of great interest to the human health. For its part, *Elaeis guineensis* x *Elaeis oleifera*-OxG [HPO] crossing palm oil hybrid is attractive for its high content of carotene (1036.9mg/100g), tocotrienols (26.4mg/100g) and monounsaturated fatty acids (MUFA) (55.8%) (Mozzon, Pacetti, Giuseppe, & Paolo, 2015; Mozzon, Pacetti, Lucci, Balzano, & Frega, 2013). However, these cultivars are not very well known to consumers, and therefore their nutritional benefits are not massively exploited.

Since actual consumers are now more worried about their diet, and expect to have more than just satisfaction, which means, some health benefit, is why FF are still a trend (Bimbo et al., 2017; Ganesan, Brodersen, & McMahon, 2014; Markey et al., 2017). FF are a healthy alternative for consumers as they provide beneficial health effects. Dairy matrices have been the most versatile, being classified as products with an adequate nutritional profile. Therefore, they can be reformulated to enhance their functional potential. For example, they can serve as a vehicle for dietary sources of tocotrienol (vitamin E) and alpha-linolenic acid (ALA). To date, the inclusion of Colombian Sacha Inchi oil (SIO) in yogurt has not been

 
Pontificia Universidad JAVERIANA Colombia
	
Research registration PUJ
	
Version: 1

Investigation project
		

investigated, nor has it been examined whether, when used as a vehicle due to its high ALA content, it exerts a beneficial effect on the cardiovascular health of consumers. On the other hand, the inclusion of Colombian hybrid palm oil has not been studied. However, it has been reported that consumption of up to 20 ml, due to its high content of gamma-tocotrienol, is a potent inhibitor of endogenous cholesterol production (Ojeda et al., 2017, 2016). To date, there are no studies investigating the effect of consuming yogurts supplemented with these Colombian oils on the cardiovascular health of consumers.

In this context of promoting healthy eating and based on the characterization of the western diet, which does not meet the daily requirements for essential fatty acids (EFAs) and fat soluble vitamins such as vitamin E, the present research project aims to describe the effect of daily consumption of two fermented dairy beverages supplemented with dietary sources high in tocotrienols and ALA on classical biological markers of cardiovascular disease (CVD) and vitamin E, over a period of three months, in individuals with cardiovascular risk. The products are currently being developed as part of a doctoral thesis in the Food Science and Technology program at the Universidad Nacional de Colombia, Bogotá campus, Faculty of Agricultural Sciences. If satisfactory results are obtained, new dairy products could be developed for the Colombian market, promoting the cultivation of Sacha INchi and Palm by diversifying the use of their fruits as sources of bioactive compounds. The present research proposal aims to answer the following question: what is the effect of consuming yogurts fortified with dietary sources of omega-3 and vitamin E on cardiovascular disease biomarkers and vitamin E in healthy adults?

OBJECTIVES

General: Evaluate the effect of consumption of two fermented dairy beverages fortified with SIO and HPO, on the lipid profile and vitamin E, in individuals at risk of CVD.

Specifics:

1. Describe the health, nutritional status and intake of the individuals before and after the intervention.
2. Establish the changes over time in the lipid profile, Apo A, Apo B and vitamin E in the blood after the intervention.

MATERIALS AND METHODS

The study will be presented to the research and ethics committee of the Faculty of Sciences of the Pontificia Universidad Javeriana. The effect of consumption of fermented dairy beverages fortified with SIO and HPO will be evaluated on the response variables: plasma lipid profile (HDL-C, LDL-C, Triglycerides, TC), Apolipoprotein A, Apolipoprotein B and vitamin E level in blood.

Type of study

An experimental study will be carried out consisting of a controlled clinical trial with three arms, each of which will be determined by the administration of two oils and a control. The oils will be transported into a fermented milk drink. Participants will be selected using a criterion of convenience through a call at the

 
Pontificia Universidad JAVERIANA Colombia
	
Research registration PUJ
	
Version: 1


Investigation project
		

Pontificia Universidad Javeriana. As a result, it is expected to select 66 individuals, 50% men and 50% women, who meet the inclusion criteria. Individuals will be stratified by sex and will be randomized in equal numbers to each of the three treatment groups, such that each treatment group will have 33 people in which the sexes will be equally distributed.

The sample size was determined taking into account the literature in which the same biomarkers have been evaluated (Brenna, Plourde, Stark, Jones, & Lin, 2018; Gonzales & Gonzales, 2014; Nayebifar, Ghasemi, & Karimipour, 2020; Qureshi, Sami, Salser, & Khan, 2001, 2002). It is important to highlight that to date there are no studies that contemplate the two oils carried in a fermented drink; even though there are studies with hybrid palm oil, alone and in other foods, there are none with Sacha Inchi oil, for the postulated response variables. Upon encountering this panorama, this study will provide a parameter to determine the sample size in subsequent studies. Finally, the postulate of the Food and Drug Administration (FDA) was taken into account, which states that the total number of subjects and patients included in Phase 1 studies varies with the drug, but is generally in the range of 20 to 80 subjects (FDA, 2019), so it is considered that it can also be applied as a criterion for foods since the guidelines for drug testing are rigorous.

Following these criteria, it was determined to take 54 subjects in total with an oversample of 20% (66 individuals in total) to compensate for possible dropouts during the follow-up stage. Compliance with the proposed number of participants and the collection of their blood samples will be subject to the evolution of the Covid-19 pandemic and government preventive isolation guidelines.

Target population

Inclusion criteria: adult men <50 years old and women <40 years old, healthy, with TC levels $\geq 200\text{mg/dl}$, with regular consumption of fermented milk beverages at least three times/week, with a maximum level of moderate physical activity and who sign the informed consent.

Exclusion criteria: TG $>700\text{mg/dl}$, hyperlipidemia undergoing pharmacological treatment, drug or alcohol addiction, smokers, history of allergy to red palm olein and/or milk and its derivatives, consumption of nutritional supplements, being pregnant or breastfeeding, having menopause, presence of chronic disease (HTN, Diabetes Mellitus, among others) and a BMI >29.9

The sample will be selected using a convenience criterion through a call at the Pontificia Universidad Javeriana. Individuals will be stratified by sex and randomized using the method called “unrestricted randomization” to the three groups. The size was determined considering the literature in which the same biomarkers have been evaluated (Brenna, Plourde, Stark, Jones, & Lin, 2018; Gonzales & Gonzales, 2014; Nayebifar, Ghasemi, & Karimipour, 2020; Qureshi, Sami, Salser, & Khan, 2001, 2002). The FDA postulate was considered, which states that the total number of subjects included in Phase 1 studies varies with the drug but is generally in the range of 20 to 80 subjects (FDA, 2019). Following these criteria, it was determined to take 54 subjects in total with an oversample of 20% (66 individuals in total), each group with 21 subjects to compensate for possible dropouts and guarantee 18 per group. Each participant must sign an informed consent.

 
Pontificia Universidad JAVERIANA Colombia
	Research registration PUJ	Version: 1
	Investigation project	

Development

The differential nutritional characteristics of the fermented milk drinks to be used in the study are presented below. It is important to clarify that all drinks will comply with current regulations for fermented drinks. (Ministerio de salud, 1986).

Table 1. Lipids and vitamin E in 200g of yogurts.

Characteristics (200g/yogurt)	Control yogurt	SIO yogurt	HPO yogurt
Total, lipids (%)	3	3	3
SFA (%)	2	7	35
MUFA (%)	0.8	10	56
PUFA (%)	0.1	85	12
Vitamin E (mg/100g)	0.06	6.09	2.88

SFA: saturated fatty acids, MUFA: monounsaturated fatty acids, PUFA: polyunsaturated fatty acids,

The analyzes of TC, c-HDL, LDL and triglycerides will be determined by the enzymatic colorimetric method; Apo A and Apo B by immunoturbidimetry and vitamin E by HPLC, in the clinical laboratory of the San Ignacio University Hospital. Each phase of the study includes supervision and support actions for participants to promote and generate adherence (Ministerio de Salud y Protección Social & Colciencias, 2014)). The intervention phase follows the recommendations of the European Food Safety Authority for claims related to cardiovascular health (Turck et al., 2018). Diagram 1 shows the study design, which consists of three phases.

Phase I

1. Screening in the anthropometry laboratory of the Faculty of Sciences of the PUJ, which consists of the following activities:
 - a. Characterization of individuals to know their sociodemographic data (age, sex, educational level, economic status).
 - b. Application of a morbidity survey, to know their diseases, clinical history, biochemical parameters, cardiovascular risk (using the Framingham risk scale)
 - c. Evaluation of body composition by dual X-ray absorptiometry - DEXA (lean mass, fat mass, bone mass, mineral density), estimation of BMI and measurement of abdominal circumference.
 - d. Exploration of eating habits (consumption frequency questionnaire and 24-hour recall).
2. Training
 - a. Record consumer diaries three days a week (two weekdays and one weekend day) and will be informed that they will receive a weekly, unannounced phone call for a 24-hour reminder and survey. about the level of physical activity.
 - b. Preparation for taking blood samples in accordance with the protocol of the San Ignacio University Hospital.

 Pontificia Universidad JAVERIANA Colombia	Research registration PUJ Investigation project	Version: 1
--	--	-------------------

[figure not shown]

Figure 1. Study design.

Phase II

The subjects will continue with their usual diet with a modification in their pattern of consumption of milk and dairy products, since fermented milk drinks will be supplied at a rate of 250g/day for one month. These will be prepared following good food handling practices (Ministerio de Salud y Protección Social, 2013), in the pilot research plant in milk and dairy products processes, of the National University of Colombia, Bogotá headquarters. All raw materials are safe for human consumption (GRAS). Through unrestricted random sampling, subjects will be assigned into three branches:

1. Control: corresponds to the subjects who will be given a fermented milk drink
2. Treatment 1 corresponds to the subjects who will be supplied with the fermented milk drink with total replacement of milk fat matter with SIO.
3. Treatment 2 corresponds to the subjects who will be supplied with the fermented milk drink with total replacement of milk fat matter with HPO.

 
Pontificia Universidad JAVERIANA Colombia
	Research registration PUJ	Version: 1
	Investigation project	

Phase III

In this phase, the results will be shared with the study participants and a final assessment.

Statistical analysis

A socio-economic-demographic characterization of the population will be carried out, by means and standard deviation and ranges. A database will be created in Excel and the intake will be analyzed using the Menus Plus 2018 software. To analyze data from blood samples, a repeated measures analysis of variance will be applied. Kolmogorov and Cramér-von Mises tests will be used to evaluate the Gaussian nature of the variables. Tukey-adjusted p values will be applied to examine differences between treatments. STATGRAPHICS CenturionXVIII software will be used.

POSSIBLE RESEARCH RESULTS

With this research, the characterization of the nutritional status, health status and quality of the diet of the target population will be obtained. Furthermore, after the intervention with fortified yogurts, it is expected to observe an improvement in the blood lipid profile parameters, Apo A, Apo B and vitamin E, of the participants compared to the initial values, which would minimize the risk of associated CVD associated to lipoproteins.

Expected products

Category	Product	Amount	Description
Other outreach products	Documentary Production	1	Submission of at least 1 scientific article in an indexed journal.
Presentation at scientific event	Presentation of paper or poster at international event	1	Participation in a conference related to the topic of clinical nutrition or food science and technology.
Project formulation and submission	Formulation and submission of other projects	1	Another project related to the characterization of the mechanism of the bioactive compound.

PARTICIPATING INSTITUTIONS

Participating entity/institution name	Temporal	Main financier	Other financier	Executor	Co-Executor	Assesment entity
UNIVERSIDAD NACIONAL DE COLOMBIA - BOGOTÁ	No	No	Yes	No	Yes	No
PONTIFICIA UNIVERSIDAD JAVERIANA (PUJ)	No	Yes	No	Yes	No	No

TEAM OF PONTIFICIA UNIVERSIDAD JAVERIANA

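### The stated group sizes of 33 and 21 both contradict the plan's 66 participants in three equal arms, which is 22 per arm

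*Combined protocol and SAP*

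**What the plan says.** Three sections of the combined protocol and SAP bear on arm size.

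- **Type of study, total and split.** "it is expected to select 66 individuals, 50% men and 50% women". These people "will be randomized in equal numbers to each of the three treatment groups". On the resulting arm size, that sentence concludes: "such that each treatment group will have 33 people in which the sexes will be equally distributed".
- **Type of study, derivation.** "it was determined to take 54 subjects in total with an oversample of 20% (66 individuals in total"; the surplus is there to cover losses during follow-up.
- **Target population.** The same derivation of 66 is repeated, and the same sentence goes on: "each group with 21 subjects to compensate for possible dropouts and guarantee 18 per group". On allocation: "Individuals will be stratified by sex and randomized using the method called"; the method it names is unrestricted randomization.
- **Phase II (under Development).** "Through unrestricted random sampling, subjects will be assigned into three branches".

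No section gives 22 per arm. There is no power calculation. The size is justified by earlier studies of the same biomarkers and by a cited Phase 1 range of 20 to 80 subjects.

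**The concern.** The plan gives one total, 66, and two arm sizes, and neither arm size agrees with that total or with the other. Someone preparing the allocation list, or an ethics committee asking how many people will be exposed, could read 63, 66 or 99. Because no significance level, power, effect size or SD is given, these counts are the only specification of sample size the plan has.

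Two further problems follow. The promise that 18 per group are guaranteed cannot be kept at 21 per group, nor at 22, because dropout is random and the plan states no rate for it. In addition, unrestricted allocation does not by itself produce the equal arms that Type of study promises, so correcting the arithmetic alone would leave a stated arm size that the stated method would rarely reach.

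**Working it through.** **Inputs from the plan:** 66 in total, half men and half women (33 of each); three arms; equal allocation; a base of 54 with a 20% oversample; 18 per group to be retained; stated group sizes 33 (Type of study) and 21 (Target population).

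**Reproducing the total.** 54/3 = 18 per arm. 18 × 1.2 = 21.6, rounded up to 22; 22 × 3 = 66. Applied to the total instead, 54 × 1.2 = 64.8, so 65, and the next multiple of three (and of six, for equal sexes) is 66. The total therefore agrees with the plan's own rule after rounding up to equal arms.

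**Testing each group size:**

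| Per group | × 3 | Against 66 | Oversample of 18 | Equal sex split possible? | Losses that still leave 18 |
|---|---|---|---|---|---|
| 33 | 99 | +33 (+50%) | 83.3% | no (odd) | 15 (45.5%) |
| 21 | 63 | −3 | 16.7% | no (odd) | 3 (14.3%) |
| 22 | 66 | 0 | 22.2% | yes (11 + 11) | 4 (18.2%) |

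33 equals 66/2, the number of each sex. No usual inflation (× 1.2 or ÷ 0.8, on the total or per arm) gives 33. 21 arises only by rounding 21.6 down. A total of 99 also lies outside the 20 to 80 range that the plan cites in support of its size.

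**Can 18 per group be guaranteed?** The plan gives no dropout rate, so the rates below are assumptions. The middle one is the loss that a 20% oversample exactly offsets: 1 − 1/1.2 = 16.7%. With independent losses, completers in an arm of n follow Binomial(n, 1 − rate), and the probability that all three arms keep at least 18 is P(X ≥ 18) cubed.

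| Assumed loss | Mean completers, 21 / 22 | P(one arm ≥ 18), 21 / 22 | P(all three ≥ 18), 21 / 22 |
|---|---|---|---|
| 10% | 18.9 / 19.8 | 0.848 / 0.938 | 61% / 82% |
| 16.7% | 17.5 / 18.3 | 0.527 / 0.700 | 15% / 34% |
| 20% | 16.8 / 17.6 | 0.370 / 0.543 | 5% / 16% |

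**Does unrestricted allocation give equal arms?** This assumes the usual meaning: each person is assigned independently with probability 1/3 to each arm. Sex strata of 33 do not change the overall distribution.

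- SD of one arm's size = √(66 × 1/3 × 2/3) = 3.83.
- P(22/22/22) = 66!/(22!³ × 3⁶⁶) = 0.0124.
- P(11/11/11 within both sexes) = 0.0246² = 0.0006.
- P(smallest arm below 18 before any dropout) = 0.350, summing the multinomial over all such splits.

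**The case against.** The total of 66 appears three times, and three equal arms make 22 easy to recover. Since 99 falls outside the plan's own cited range, 33 reads as a slip and not as a rival design, and 21 differs from 22 by one person per arm. No stated power depends on any of these figures, and enrolment is in any case made subject to the pandemic. That bears on how much harm results. It does not reconcile the figures, and a slip in a stated sample size still has to be corrected.

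Several narrower points do stand:

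- 66 is not exactly 54 plus 20%. It is a 22.2% oversample, and rounding each arm up is an inference that the plan does not spell out. So 22 is derived, and the sponsor should confirm it.
- The promise of equal sexes within a group is attached to 33. The text giving 21 says only that allocation is stratified by sex, so the odd number counts against 21 only if the two sections are read together.
- That 33 is the per-sex count written in the wrong place is plausible but not documented.
- The allocation probabilities depend on simple randomisation. If the wording means a random draw into fixed, equal arm sizes, the 1.2% and 35% no longer apply. The text then needs to say so, because unrestricted randomisation ordinarily means the opposite.
- The completer figures rest on assumed dropout rates. They show that 18 is not guaranteed; they do not predict what will happen.

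**Conclusion.** The concern holds and needs correction. The plan's figures imply totals of 66, 99 and 63, which cannot all be right. The 33 overstates the total by half; the 21 understates it by three and falls short of the plan's own oversample. The only arm size that fits 66 people, three equal arms and an equal sex split is 22. This part is plain arithmetic on the plan's numbers and needs no assumption beyond taking 66, the only total stated, as intended.

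The statement that 18 per group are guaranteed is unsupported at either 21 or 22; how far it fails depends on a dropout rate that the plan does not give. The conflict between equal numbers and unrestricted allocation is a real conflict of wording. Its numerical size is conditional on simple randomisation.

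**What to change.** 1. In Type of study and in Target population, state one figure: 66 randomised, 22 per arm. Delete 33 and 21. The sponsor should confirm that 66 is the intended total.
2. Replace the guarantee with wording such as: about 18 completers expected per arm if dropout is no more than about 17–18% (at most 4 of 22). Label any other dropout rate as an assumption.
3. Reconcile the allocation wording in Target population and Phase II with Type of study. The preferred route, since equal numbers are promised, is a list balanced within sex: 11 men and 11 women per arm if 33 of each sex are recruited. The alternative is to keep unrestricted allocation and change Type of study to about 22 per arm, without promising equality by arm or sex. If allocation has already been done, describe the method actually used.

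**Cost.** This is a change of wording and, if chosen, a balanced list; nobody beyond the planned 66 is enrolled. The stated expectation of completers becomes slightly less favourable. With a balanced list, the last assignments in a block are easier to guess unless the block order is concealed, and the 11 + 11 split holds only if recruitment reaches 33 of each sex.

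### The allergy exclusion names palm olein and milk but not Sacha Inchi, so a person with a known allergy to one of the two test oils could be randomised to it

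*Combined protocol and SAP*

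**What the plan says.** Under Target population, the exclusion criteria contain one allergy item: "history of allergy to red palm olein and/or milk and its derivatives". The same list excludes "presence of chronic disease (HTN, Diabetes Mellitus, among others"), along with items on lipids, medication, smoking, supplements, pregnancy, menopause and BMI.

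Phase II describes three arms. Control participants receive a fermented milk drink. Treatment 1 is a "fermented milk drink with total replacement of milk fat matter with SIO". Treatment 2 is a "fermented milk drink with total replacement of milk fat matter with HPO". The Type of study section has participants "randomized in equal numbers to each of the three treatment groups", and Phase II states that "fermented milk drinks will be supplied at a rate of 250g/day for one month".

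Phase I screening includes "Application of a morbidity survey, to know their diseases, clinical history, biochemical parameters, cardiovascular risk". Phase II also states that the raw materials are generally recognised as safe for people to eat.

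**The concern.** The protocol chose to screen for allergy ingredient by ingredient, and the list of ingredients is one short. Consent and eligibility are settled before allocation, so every participant must be fit to receive any of the three drinks. The criterion checks this for the milk base and for palm, but not for the oil that defines the SIO arm.

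What is at stake is first the safety of a participant who already knows of a Sacha Inchi allergy. A lesser consequence is that any withdrawal caused by a reaction to that oil would fall in one arm only, in a trial that aims to finish with 18 people per group.

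**Working it through.** No sample size, power or error-rate calculation applies. The check is a comparison of the eligibility list with the products, followed by a search for any other safeguard.

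**1. Ingredients against the allergy criterion**

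| Component | Given in | Named in the allergy exclusion? |
|---|---|---|
| Fermented milk base | All three arms | Yes |
| Palm oil (HPO) | Treatment 2 | Yes, taking red palm olein to stand for the palm product |
| Sacha Inchi oil (SIO) | Treatment 1 | No |

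**2. Could another provision cover it?**

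- *Requirement to be healthy, and the chronic disease exclusion.* Neither names allergy; the examples given are hypertension and diabetes. Because palm and milk allergy are listed separately, the protocol evidently did not rely on these terms to catch food allergy.
- *Morbidity survey.* It gathers diseases and clinical history. An allergy might come to light there, but no rule says that a Sacha Inchi allergy would then exclude the person.
- *Regular consumption of fermented milk drinks (inclusion criterion).* This gives some reassurance about tolerance of milk and none about Sacha Inchi.
- *General food-safety statement.* It applies to all raw materials, palm and milk included, yet the protocol still excludes people allergic to those two. It therefore does not replace an individual allergy screen.

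None of these closes the gap.

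**3. Chance of assignment and exposure**

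- Equal allocation to three arms gives a nominal probability of 1/3 for SIO.
- With 66 enrolled: 66 / 3 = 22 people in the SIO arm. The protocol's own per-arm figures do not agree with this: Type of study gives 33 per group (3 × 33 = 99) and Target population gives 21 (3 × 21 = 63). It also names unrestricted randomisation, under which arm sizes can vary. The nominal 1/3 does not depend on which arm size is right.
- Daily oil intake, assuming that the 3% total lipids in Table 1 is by weight: 250 g × 0.03 = 7.5 g per day. Phase II sets the duration at one month; the introductory text speaks of three months. On either reading the exposure is daily and repeated.

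**4. Expected number affected**

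This would be the number enrolled × the prevalence of known Sacha Inchi allergy × 1/3. The documents give no prevalence, so the product cannot be evaluated.

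**The case against.** The strongest reply is that the exclusion list is not the whole of screening. Candidates must be healthy, must sign consent, and go through a morbidity survey, a food-frequency questionnaire and a 24-hour recall. Someone who knows of an allergy has several chances to say so, and an investigator would be likely to act on it. The consent form and the survey questionnaire are not in the available text, so a warning or an allergy question there cannot be ruled out. This stands to the extent that the protocol *could* admit such a person, not that it certainly would. It does not remove the mismatch: a warning elsewhere would not make the eligibility rule agree with the products.

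A second reply is that few people are likely to be affected. The protocol itself says that these crops are little known to consumers, and people who have rarely eaten a food seldom have a recognised allergy to it. That is a fair inference and limits the expected count. The same unfamiliarity cuts the other way on screening, because participants may not think to mention Sacha Inchi unless asked.

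Third, 22 of 66 describes the size of an arm, not the size of the risk, and no effect on estimates or power has been shown. Both points are accepted.

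**Conclusion.** The concern holds. The allergy exclusion leaves out one of the two test oils, and nothing else in the available text excludes a person with a known Sacha Inchi allergy before randomisation. Such a person would have a nominal 1 in 3 chance of daily exposure.

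The omission in the wording is certain. The number of people it would affect is unknown and may be very small. The conclusion assumes that the eligibility list as shown is complete and that allocation is equal across arms. It would be softened, though not reversed, if the consent form or survey already asks about Sacha Inchi. Sample size and analysis are unaffected. The change should be made because the possible harm falls on participants and the correction is nearly free.

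**What to change.** Reword the allergy item in the exclusion criteria so that it covers every ingredient of the three study drinks, with Sacha Inchi named alongside palm and milk. Confirm that the Phase I morbidity survey has a matching question, and add one if it does not. The investigators should set the clinical wording, including whether related seed allergies belong in it.

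The cost is one phrase in the criteria and at most one question at screening, with a negligible effect on recruitment.
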